5.2 Enrollment and Retention of Study Population

5.2.1 Recruitment Procedures

Before the start of the study, the Investigator or delegate will contact an appropriate pool of potential subjects or parent of potential subjects and invite them to participate in the study. The site will ensure that any advertisements used to recruit subjects (letters, pamphlets, posters) are submitted to the Sponsor prior to submission to the IEC/ IRB for approval.

Recruitment procedures and materials will be submitted for IEC/ IRB approval or favorable opinion before implementation.

5.2.2 Informed Consent Procedures

Informed consent is the process by which a subject and/or an appropriate and LAR voluntarily confirms his or her willingness to participate or let his/her child participate in a particular study. Informed consent must be obtained before any study procedures are performed. The process is documented by means of a written, signed, and dated ICF and /or AF. A separate AF will be provided for subjects aged 13 to less than 18 years or for subjects aged 7 to 12 years. The AF is in addition to, not in place of, an ICF that is signed by the parent/ LAR.

In accordance with GCP, prior to signing and dating the consent form, the subject and/or parent/LAR must be informed by appropriate study personnel about all aspects of the study that are relevant to making the decision to participate and must have sufficient time and opportunity to ask any questions.

The actual ICF and AFs used at each center may differ, depending on local regulations and IEC/ IRB requirements. However, all versions must contain the standard information found in the sample ICF provided by the Sponsor. Any change to the content of the ICF must be approved by the Sponsor and the IEC/ IRB prior to the form being used.

If new information becomes available that may be relevant to the subject's or LAR's willingness to continue participation in the study, this will be communicated to him/ her in a timely manner. Such information will be provided via a revised ICF or an addendum to the original ICF and via a revised AF or an addendum to the original AF.

Informed consent forms and AFs will be provided in duplicate, or a photocopy of the signed consent will be made. The original will be kept by the Investigator, and the copy will be kept by the subject or subject's parent/LAR.

Documentation of the consent process should be recorded in the source documents.

In the context of this clinical study, subject will be receiving different vaccination regimens, ie, 2- or 3-dose PrEP regimen. Subject has the chance of receiving vaccine not yet licensed (VRVg-2) or the vaccine that was previously licensed in Thailand (Imovax® Rabies) or currently licensed there (Verorab®). In addition, subject or subject's parent/LAR needs to give consent and comply with other study-related activities which are not usually part of the treatment process, ie, blood draws, filling up of DCs, MA, scheduled visits, phone calls from study staff and, if woman of childbearing potential, other procedures such as urine pregnancy test before each vaccination or

follow-up of the subject's health and the newborn's health in case of pregnancy will be carried out.

5.2.3 Screening Criteria

There are no screening criteria other than the inclusion and exclusion criteria.

5.2.4 Inclusion Criteria

An individual must fulfill *all* of the following criteria to be eligible for study enrollment:

- 1) Aged \geq 1 year on the day of inclusion^a
- 2) ICF has been signed and dated by the subject and/or parent(s) or LAR and by an independent witness (if required by local regulations), as necessary; and AF has been signed and dated by the subject, as required
- 3) Subject (adult \geq 18 years) or subject and parent/LAR (1 year to $<$ 18 years) are able to attend all scheduled visits and to comply with all study procedures.

5.2.5 Exclusion Criteria

An individual fulfilling *any* of the following criteria is to be excluded from study enrollment:

- 1) Subject is pregnant, or lactating, or of childbearing potential and not using an effective method of contraception or abstinence from at least 4 weeks prior to the 1st vaccination and 1 month after each vaccination. To be considered of non-childbearing potential, a female must be pre-menarche^b or post-menopausal for at least 1 year, or surgically sterile.
- 2) Participation at the time of study enrollment or, planned participation during the present study period in another clinical study investigating a vaccine, drug, medical device, or medical procedure.
- 3) Receipt of any vaccine in the 4 weeks (28 days) preceding the 1st study vaccination or planned receipt of any vaccine prior to V05 for pediatric subjects and adult subjects in Cohort 1, and prior to V04 for adult subjects in Cohort 2.
- 4) Previous vaccination against rabies (in pre- or post-exposure regimen) with either the study vaccines or another vaccine.
- 5) Bite by, or exposure to a potentially rabid animal in the previous 6 months with or without PEP.
- 6) Receipt of immune globulins, blood or blood-derived products in the past 3 months.

^a " \geq 1 year" means from the day of the 1st birthday onwards, with no upper age limit

^b Pre-menarche females will declare by themselves that they have not yet started menstruation. If a young female subject reaches menarche during the study, then she is to be considered as a woman of childbearing potential from that time forward.

- 7) Known or suspected congenital or acquired immunodeficiency; or receipt of immunosuppressive therapy, such as anti-cancer chemotherapy or radiation therapy, within the preceding 6 months; or long-term systemic corticosteroid therapy (prednisone or equivalent for more than 2 consecutive weeks within the past 3 months).
- 8) At high risk for rabies exposure during the study^a.
- 9) Known systemic hypersensitivity to any of the study/control vaccine components, or history of a life-threatening reaction to the vaccines used in the study or to a vaccine containing any of the same substances^b.
- 10) Self-reported thrombocytopenia, contraindicating IM vaccination.
- 11) Bleeding disorder, or receipt of anticoagulants in the 3 weeks preceding inclusion, contraindicating IM vaccination.
- 12) Deprived of freedom by an administrative or court order, or in an emergency setting, or hospitalized involuntarily.
- 13) Current alcohol or substance abuse that, in the opinion of the Investigator, might interfere with the study conduct or completion.
- 14) Chronic illness that, in the opinion of the Investigator, is at a stage where it might interfere with study conduct or completion^c.
- 15) Moderate or severe acute illness/infection (according to Investigator judgment) on the day of vaccination or febrile illness (temperature $\geq 38.0^{\circ}\text{C}$). A prospective subject should not be included in the study until the condition has resolved or the febrile event has subsided.
- 16) Personal History of Guillain-Barré syndrome.
- 17) Identified as an Investigator or employee of the Investigator or study center with direct involvement in the proposed study, or identified as an immediate family member (ie, parent, spouse, natural or adopted child) of the Investigator or employee with direct involvement in the proposed study.

If the subject has a primary physician who is not the Investigator, if feasible the site should contact this physician with the subject's consent to inform him/ her of the subject's participation in the study. In addition, the site should ask this primary physician to verify exclusion criteria relating to previous therapies, such as receipt of blood products or previous vaccines.

^a Such as veterinarians and their staff, animal handlers, rabies researchers, and certain laboratory workers.

^b The components of VRVg-2 are listed under Section 6 Investigational Product and in the Investigator's Brochure Section 3.2. The components of Verorab and Imovax Rabies vaccines are listed under Section 6 Control Products, eg, traces of polymyxin B, streptomycin, or neomycin.

^c Chronic illness may include, but is not limited to, neurological, cardiopulmonary, gastrointestinal, renal, genitourinary, metabolic, hematologic, auto-immune, or psychiatric disorders or infection.

5.2.6 Medical History

Prior to enrollment, subjects will be assessed for pre-existing conditions and illnesses, both past and ongoing. Any such conditions will be documented in the source document. Significant (clinically relevant) medical history (reported as diagnosis) including conditions/illnesses for which the subject is or has been followed by a physician or conditions/illnesses that could resume during the course of the study or lead to an SAE or to a repetitive outpatient care will be collected in the case report book (CRB). The significant medical history section of the CRB contains a core list of body systems and disorders that could be used to prompt comprehensive reporting, as well as space for the reporting of specific conditions and illnesses.

For each condition, the data collected will be limited to:

- Diagnosis (this is preferable to reporting signs and symptoms)
- Presence or absence of the condition at enrollment

The reporting of signs and symptoms in lieu of a diagnosis is strongly discouraged.

Dates, medications, and body systems are not to be recorded, and the information collected will not be coded. Its purpose is to assist in the later interpretation of safety data collected during the study. Given the current COVID-19 pandemic, the medical history must actively include if suspected/ confirmed COVID-19 happened and the dates. The use of medications (prescribed or out-of-the-counter) such as chloroquine and hydroxychloroquine within at least 2 months before enrollment and during the conduct of the study should be recorded, given their interference with rabies vaccines (38).

5.2.7 Contraindications for Subsequent Vaccinations

5.2.7.1 Temporary Contraindications

Should a subject experience one of the conditions listed below, the Investigator will postpone further vaccination until the condition is resolved. Postponement must still be within the timeframe for vaccination indicated in the [Table of Study Procedures](#) (except for VAC2 in Cohort 2 which can be given after resolution of temporary contraindication(s) to permit the subject fully benefit from the rabies vaccination). If any dose is delayed, the subsequent doses should be delayed according to the original time interval.

- Moderate or severe acute illness/infection (according to Investigator judgment) on the day of vaccination or febrile illness (temperature $\geq 38.0^{\circ}\text{C}$).
- For Primary Series Cohort 2: unplanned administration of a vaccine other than the study vaccine between D0 and last primary vaccination (D07-VAC2). Since this is a PrEP study and the subjects will benefit from the rabies vaccination, the subject can receive the 2nd rabies primary dose at least 4 weeks after receipt of another vaccine (out of window) but will be excluded from the Per-Protocol Analysis Set (PPAS) – see [Section 12.2.4](#).
- For Immunogenicity Persistence and Booster Phase Cohort 2: administration of a vaccine other than the study vaccine 4 weeks prior to or planned administration within 4 weeks after booster vaccination, only if the delayed booster vaccination can still be maintained within the

allowed time window (M24-36 +14 days). If the allowed time window cannot be applied; please refer to [Section 5.2.7.2](#).

- Note: Vaccinations other than study vaccine consist of prohibited therapies within 28 days before and after each study vaccination ([Section 6.9](#)), their administration results in exclusion from PPAS and protocol deviation. The decision whether or not this would consist of a significant non-compliance with the protocol (condition for withdrawal from the study) depends on Investigator's judgment. There are no restrictions for receipt of other vaccines, including COVID-19 vaccination, in other study time frames: between V05 (Cohort 1) or V04 (Cohort 2) and 4 weeks before booster visit, or > 28 days after booster vaccination.

5.2.7.2 Definitive Contraindications

Should a subject experience 1 of the conditions listed below, the Investigator will discontinue vaccination:

- Pregnancy, as indicated by a positive urine test.
- Anaphylactic or other significant allergic reaction to the previous dose of vaccine.
- Immunoglobulin, blood or blood-derived products received in the past 3 months or ongoing at the visit.
- Immunosuppressive therapy such as anti-cancer chemotherapy or radiation therapy in the past 6 months or ongoing at the visit, or long-term systemic corticosteroid therapy (for more than 2 consecutive weeks in the past 3 months before the visit).
- Human immunodeficiency virus (HIV) seropositivity.
- Thrombocytopenia, bleeding disorder or receipt of anticoagulants contraindicating IM vaccination.
- For Primary Series Cohort 1: administration of a vaccine other than the study vaccine between D0 and last primary vaccination (VAC3) or planned administration before V05.
- For Booster Phase Cohort 1: administration of a vaccine other than the study vaccine 4 weeks prior to or planned administration within 4 weeks after booster vaccination.
- For Immunogenicity Persistence and Booster Phase Cohort 2: administration of a vaccine other than the study vaccine 4 weeks prior to or planned administration within 4 weeks after booster vaccination, only if the temporary contraindication for the booster (see [Section 5.2.7.1](#)) could not be applied since it would not permit to keep visits schedule within the allowed window.
- An SAE related to the study vaccines following a vaccination.
- Any potential contact with rabies virus during the course of the study.
- Reporting of Guillain-Barré syndrome.

Subjects with a definitive contraindication will continue to be followed up for the study-defined safety and immunogenicity assessments, as applicable.

5.2.8 Coronavirus Disease 2019 (COVID-19) Vaccine

Should the COVID-19 vaccination campaign be implemented during the study for the population eligible to participate or participating in the study, applicable country recommendations will be implemented. If a subject is eligible to participate, it is recommended the subject prioritize the COVID-19 vaccination and delay the time of the enrollment according to the exclusion criterion specified in [Section 5.2.5](#). If the subject was already enrolled in the study, when possible and unless recommended otherwise, as per national public health policies or Investigator judgment, a 4-week interval between any study vaccine dose and the COVID vaccine dose(s) is desirable.

When the subject is already enrolled in the study if a COVID-19 vaccine dose is received during one study vaccine solicited reactogenicity period it would not be possible to differentiate systemic reactions between them. Likewise, if the COVID-19 vaccine is received between a study vaccine dose and the collection of blood, it will not be possible (at this point) to rule out an immunogenicity interaction. Therefore, in any of the 2 situations, it is recommended that the subject will not be withdrawn from the study and should continue within the full analysis set (FAS).

The type of COVID-19 vaccine received (including tradename) and the date/time of its administration(s) should be documented in the concomitant medications CRF.

Wherever possible, the site of injection of study vaccines should be in the limb separate from the limb in which the COVID-19 vaccine is administered (if it has already been administered). Likewise, and if on the control of the study site, any COVID-19 vaccine scheduled to be received after administration of study vaccines should not be received in the same limb as study vaccines. Where it is not possible to have study vaccines and COVID-19 vaccine administered in separate limbs, a distance of at least 1 inch/ 2.5 cm should be maintained between the 2 administration sites.

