#### 5.1.3.2 Impact of the COVID-19 pandemic

To evaluate the possible impact of the COVID-19 pandemic on the study conduction, main immunogenicity and safety results, the following sensitive analyses will be performed but not limited to:

- Impact of COVID-19 pandemic on subject's disposition, based on enrolled subjects

Note: Subjects impacted by COVID-19 refers to subjects with at least one major/critical protocol deviation due to COVID-19, or who did not complete the study due to COVID-19, or who reported "VISIT NOT DONE" on safety follow up in pandemic form.

- Major or critical deviations due to COVID-19 by randomized group, based on randomized subjects.
- Immunogenicity analysis primarily based on FASI, FASI for Immunogenicity Persistency and FASI for Booster
  - Impact of COVID-19 pandemic on immunogenicity analysis.
  - Impact of medical history of suspected/confirmed COVID-19 pandemic on immunogenicity analysis.
  - Impact of the use of concomitant medications that are used during the study/or were used within 2 months before enrollment for treating/preventing COVID-19 (ie, Hydroxychloroquine and chloroquine) on immunogenicity.

- If any subjects received at least one dose of vaccination but took any concomitant medications for treating/preventing COVID-19 (ie, Hydroxychloroquine and chloroquine) within 2 months before enrollment, then the following immunogenicity analysis will be conducted based on PPAS
  - Immunogenicity of subjects who did not take any concomitant medications for treating/preventing COVID-19 (ie, Hydroxychloroquine and chloroquine) within 2 months before enrollment.
- Safety analysis based on SafAS and SafASB
  - Impact of COVID-19 pandemic on safety overview up to 28 days after any vaccination.
  - Impact of medical history of suspected/confirmed COVID-19 pandemic on safety overview up to 28 days after any vaccination.
  - Impact of the use of concomitant medications that are used during the study/or were used within 2 months before enrollment for treating/preventing COVID-19 (ie, Hydroxychloroquine and chloroquine) on safety overview up to 28 days after any vaccination.

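### Protocol 5.2.7 makes the 4-week gap between a COVID-19 vaccine and the Cohort 2 booster binding, 5.2.8 makes it advisory, and no named analysis isolates reactions after overlapping doses

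*Protocol*

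**What the plan says.** **The binding rule.** Protocol 5.2.7.1 lists temporary contraindications, for which "the Investigator will postpone further vaccination until the condition is resolved". For the Cohort 2 booster the trigger is "administration of a vaccine other than the study vaccine 4 weeks prior to or planned administration within 4 weeks after booster vaccination". Postponement applies "only if the delayed booster vaccination can still be maintained within the" allowed window of M24-M36 plus 14 days. Failing that, Section 5.2.7.2 makes the same event a definitive contraindication, for which "the Investigator will discontinue vaccination". The note closing 5.2.7.1 adds: "Vaccinations other than study vaccine consist of prohibited therapies within 28 days before and after each study vaccination". It attaches exclusion from the PPAS and a protocol deviation to any breach, and it brings COVID-19 vaccine into scope by freeing it only elsewhere: "There are no restrictions for receipt of other vaccines, including COVID-19 vaccination, in other study time frames".

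**The advisory rule.** Protocol 5.2.8 says of enrolled subjects that "a 4-week interval between any study vaccine dose and the COVID vaccine dose(s) is desirable", where possible and unless national policy or the investigator's judgment points otherwise. It gives instructions on separate limbs, or 2.5 cm spacing in one limb. It says that systemic reactions cannot be told apart if a COVID-19 dose falls in the solicited period, and it keeps such a subject in the study and in the FAS.

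**The analysis.** Protocol 9.2.1.1 and SAP 5.3.2.2 treat every solicited systemic reaction as related to study vaccination. Protocol 12.2.2 and SAP 5.2.3 put everyone who was boosted in the SafASB. SAP 5.1.3.2 plans COVID-19 analyses by pandemic impact, COVID-19 history and chloroquine or hydroxychloroquine use. It defines impact partly by deviations: "Subjects impacted by COVID-19 refers to subjects with at least one major/critical protocol deviation due to COVID-19".

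**The concern.** Two parts of one protocol give the same 4-week interval different force, and the choice decides whether a booster is given close to a COVID-19 vaccine. The estimate exposed is the rate of solicited systemic reactions after the VRVg-2 booster. If a COVID-19 dose falls close to the booster, its fever, headache, malaise and myalgia enter that rate as VRVg-2 reactions. All six primed groups receive VRVg-2 as booster, so no concurrent comparator vaccine carries the same contamination and offsets it. The same can happen after primary-series doses, but there randomised control vaccines give some protection. Overlap could also affect post-booster titres in FASB2 and FASIB2, since Section 5.2.8 says an interaction cannot be ruled out.

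**Working it through.** No power or alpha figure is in dispute, so the main check compares the texts. The arithmetic only bounds the effect.

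**1. Does the binding rule cover COVID-19 vaccine?** Yes. The 5.2.7.1 note lifts restrictions on other vaccines, naming COVID-19 vaccination, only outside the 28-day periods around study doses.

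**2. Is there a precedence rule?** No. The prohibition in 5.2.7.1 cites Section 6.9 for its detail, and Section 6.9 refers COVID-19 vaccine use to Section 5.2.8. A reader who follows the cross-references ends at the advisory text.

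**3. Is 5.2.8 only about what to do after an accidental overlap?** Not wholly. Its limb instructions say where to place the study vaccine when a COVID-19 vaccine has already been given, which contemplates study dosing soon after one.

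**4. How often would the binding rule end in no booster?** M24 to M36 plus 14 days is about 365 + 14 = 379 days. A wait of up to 28 days after a COVID-19 vaccine overruns only for boosters due in about the last 28 days: 28/379 = 7.4%, assuming visits spread evenly. A COVID-19 dose planned for up to 28 days ahead, followed by 28 days' wait, could need 56 days: 56/379 = 14.8%. So most subjects would be boosted under either section. What usually differs is delay against overlap.

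**5. Size per overlap.** The plan's evaluable counts reproduce: 230 × 0.85 = 195.5 (stated 195) and 138 × 0.85 = 117.3 (stated 117). One overlapping dose that turns a non-reactor into a reactor adds:

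- overall: 1/195 = 0.5 percentage points
- VRVg-2-primed group: 1/117 = 0.85 points
- one control-primed group: 46 × 0.85 ≈ 39, and 1/39 = 2.6 points

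These are ceilings, because some subjects would have reacted anyway. If p is the reaction rate without COVID-19 vaccine and q the chance that the COVID-19 vaccine causes a reaction in a non-reactor, the expected addition per overlap is (1 − p)q/N. With assumed values not in the documents, p = 20% and q = 30% to 60%, the overall figure is 0.8 × 0.3/195 = 0.12 to 0.8 × 0.6/195 = 0.25 points.

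**6. Would the SAP show it?** Only indirectly. An overlap enters the impacted group if it is graded a major or critical deviation and attributed to COVID-19. Section 5.2.7.1 calls it a deviation, whereas Section 5.2.8 makes the interval only advisory. SAP 5.1.3.2 also replaces tables by listings when fewer than 5% of randomised subjects are impacted. On the 230 planned Cohort 2 booster subjects that is 0.05 × 230 = 11.5, so 11 or fewer impacted subjects would give listings only.

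**The case against.** Several counter-arguments have force.

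- **Compliance with both sections is possible.** A reader might infer that a site cannot follow both. That is wrong: a site that always keeps 4 weeks satisfies both. What stands is that a site relying on 5.2.8 may breach 5.2.7.
- **Postponement comes first.** A reader might also infer that, under 5.2.7, the subject goes unboosted and drops out of FASB2 and SafASB. For the Cohort 2 booster that is the exception, as step 4 shows. Section 5.2.7.2 stops the dose directly in Cohort 1, whose booster phase is over.
- **Immunogenicity has a safeguard.** The booster PPAS excludes subjects with a prohibited vaccine before V09 (Protocol 12.2.3.4, SAP 5.2.2.4). Remaining in the FAS while leaving the PPAS is consistent. FASB2 and FASIB2 keep these subjects, however, and SAP 5.2.5 plans booster analyses on both.
- **The SAP is not silent.** Its COVID-19 list is expressly open-ended and includes a pandemic-impact safety overview on SafAS and SafASB. That overview is not specific to vaccination and may shrink to listings.
- **Attribution is not automatic for everything.** Unsolicited systemic events receive an investigator's causality judgment, and separate limbs limit confusion of local reactions. The difficulty lies mainly with solicited systemic reactions in D0-D7.
- **No hypothesis test depends on it.** Booster results are descriptive. The primary and five key secondary tests are analysed mainly on the D42 and D28 PPAS.

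These points narrow the consequence. They do not supply the missing precedence rule.

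**Conclusion.** The inconsistency is real, and its reach is limited. Sections 5.2.7.1 and 5.2.7.2 bind where Section 5.2.8 only advises, Section 6.9 points to the latter, and neither is said to prevail. The same Cohort 2 subject can therefore be delayed or dosed with overlap, depending on the section applied.

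The exposure is confined to descriptive reactogenicity, chiefly after the booster, and to FASB2 and FASIB2 titres. Each overlap moves the booster systemic reaction rate by at most 0.5 points overall and 0.85 points in the VRVg-2-primed group, taking the planned 195 and 117 evaluable subjects. No total can be given, because the documents do not say how many overlaps occurred or whether any did. A reader should not infer material bias in the booster results, or any threat to the confirmatory conclusions. The documents support neither.

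**What to change.** **Protocol.** The sponsor should reconcile Sections 5.2.7.1, 5.2.7.2, 5.2.8 and 6.9 and state which section governs COVID-19 vaccination around each study dose. Which clinical rule to adopt is for the sponsor and investigators, and this review takes no position on it.

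**SAP 5.1.3.2.** Add one supplementary summary of solicited systemic reactions, on SafAS and SafASB, that omits doses with a COVID-19 vaccine in the 7 days before or after the study dose. Show it beside the full-set result, with the number of doses omitted per group, and produce it regardless of the 5% listing rule.

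**Cost.** A wording change and one table with a slightly smaller denominator. No new data are needed, because Section 5.2.8 already asks for the COVID-19 vaccine's type and date in the concomitant medication CRF.
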